2.2. Safety Outcomes Measured

- i. Adverse events, serious adverse events (SAEs),
- ii. Suspected adverse drug reactions

3. INVESTIGATIONAL PLAN

3.1. Study Design

This is a prospective, randomized, single-blind, active control trial for patients undergoing elective lobectomy. Subjects will be randomly assigned to receive either liposomal bupivacaine (Exparel, test group A) or standard bupivacaine HCl with epinephrine (Marcaine, active comparator group B) during surgery. Pain management will be monitored via opioid usage and visual pain assessment throughout the hospital stay and at postoperative day 30, 6 month and 1 year follow up visits. Overall study schema is described in Figure 1 at the end of this document

3.2. Clinical Setting:

Study will be conducted at SIU-Medicine Clinics and Memorial Medical Center.

3.3. Patient population

Study population includes patients undergoing elective standard of care lobectomy. Based on our power analysis, 150 subjects (75 in each randomized group) need to be included (see *Section 5, Statistical Analyses*). Taking into consideration a potential loss of 50 patients due to withdrawal, lost to follow up or other reasons, 200 patients will initially be enrolled and randomized to attain 150 evaluable subjects at the end of study (1-year follow up). We estimate this study will take up to three years to complete our enrollment.

3.3.1. Inclusion Criteria

1. Adult at least 18 years of age
2. Subject needs elective lobectomy for NSCLC
3. Willing to comply with all aspects of protocol, including providing information about opioid usage for post-surgical pain and signed informed consent

3.3.1. Exclusion Criteria:

1. < 18 years of age, > 80 years of age
2. Inability or unwillingness to consent
3. Emergency surgery

4. Previous ipsilateral thoracic surgery
5. Need for operative pleurectomy or pleurodesis as the primary operation
6. Chronic Narcotic use for 6 or more months
7. Any extensive narcotic use in the 1 month period prior to screening with an exception for the use of narcotics commensurate with standard care diagnostic procedures for VATS Lobectomy
8. Allergies to bupivacaine or other local anesthetics, narcotics, NSAIDs or acetaminophen
9. Moderate to severe hepatic impairment (ALT or AST) value greater than 3 times the upper limit of normal.
10. Severe renal impairment or end stage renal failure disease (creatinine greater than 2.0 mg/dl).
11. History of peptic ulcerative disease
12. Severe chronic obstructive pulmonary disease (COPD) due to LVRS (lung-volume reduction surgery).
13. Pregnancy
14. Need for conversion from a Video-Assisted Thoracic Surgery procedure to an open thoracotomy
15. Subjects who are incarcerated
16. Subject has been treated with an experimental device within 30 days or received an experimental agent within the longer of 30 days or five half-lives. Or subject is current enrolled in another clinical trial.
17. Unable to follow protocol directions due to organic brain or psychiatric disease.
18. History of alcoholism or any other substance abuse, which, in the opinion of the investigator, would affect compliance with the protocol.

3.4. Study procedures

3.4.1. Summary

All patients scheduled for surgical consult with Cardiothoracic Surgery for possible VATS lobectomy will be prescreened for initial eligibility criteria. Subjects who elect to go forward with surgery will be presented with the opportunity to participate in the study. Informed consent form will be discussed in detail at the clinic or MMC (for in-patient potential subjects) by authorized study personnel. Patient will be given time to review the informed consent with family if so desired. After the patient voluntarily agrees to participate (sign ICF), their inclusion/exclusion criteria will be reviewed again

based on SOC testing to ensure continued eligibility. Patient data such as vitals, physical examination (PE), medications, and medical and surgical history will be recorded or obtained from the EHR. Subjects will be randomized to one of two groups, test (A) and active control (B), Night or morning of scheduled surgery. At the end of surgery, study drug will be administered as described in details below per the standard FDA guidelines. Outcomes will be measured during post-operative hospital stay and until 1 year after surgery for extended follow up which is the standard protocol with CT surgery. A schedule for all assessments throughout the study is described in table 1 at the end of this document.

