3.4.4. Method of treatment assignment/Randomization

(1) Subject Numbering

Subjects will be assigned a unique consecutive subject number, 3 digits. Preceding the digits will be the letters EM (Exparel/Marcaine) to identify the study. For example, subject numbers will be EM001, EM002, etc., in consecutive order. Subject numbers, once assigned, will not be reused.

(2) Randomization

A randomization schema will be performed by a secondary statistician at the Centers for Clinical Research for all 200 patients and will be listed on one list that will be provided to MMC pharmacy and will also be stored by the Research Coordinators for reference. The patient ID and randomization assignment will be sent to the pharmacy along with screening weight of the subject. The subject(s) and study statistician(s) will remain blinded to the treatment assignments throughout the course of the study while the surgical team and coordinators will not be blinded. Data will be analyzed by the blinded statistician(s) to ensure minimal bias.

(3) Administration and timing of Study drug

Study drug will be administered by the investigator surgeon or members of surgical team under supervision of the investigator surgeon as described below:

Test group A: At the end of the surgical procedure patients in group A will receive injections of liposomal bupivacaine (Exparel, standard dose based on patient's screening weight) delivered via a 25 gauge needle into the surrounding cutaneous and deep tissue including the periosteum around the thoracoscopic port incision sites after closure.

Active Comparator Group B: At the end of the surgical procedure patients in group B will receive, injections of standard bupivacaine HCl with epinephrine 0.25% delivered via 25 gauge needle into the surrounding cutaneous and deep tissue including the periosteum around the thoracoscopic port incision sites after closure.

- *Rationale for Selection of Doses*

Dose will be calculated by the physician based on the screening weight of each randomized patient as is done in the standard way. This will provide reasonable comparison of standard dose of each drug that would have been given for any individual patient.

(4) Treatment compliance

Treatment compliance will be measured in terms of the subject receiving an injection of either Exparel® or Marcaine with epinephrine® from the study personnel. No other forms of compliance will be measured.

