3.4.6. Concomitant Medications during the Study

(1) Prohibited Concomitant Medications Prior to Study Treatment:

Any chronic/habitual use of narcotics or within one period before consent and screening will be exclusionary. Any use of narcotics between screening and operative day, will be classified as screen failure (if not randomized) or withdrawn (if randomization has been done).

(2) Concomitant Medications during the Study

Details of all home medications, pain management medications, and anti-nausea medications will be recorded.

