7. ASSESSEMENT OF SAFETY

Stopping rules and attributes of seriousness, unexpectedness, severity and causality will be assigned by the investigators and further reviewed during monthly meetings, or as needed based on urgency, as part of the data and safety monitoring plan (DSMP).

Summary: Screening eligibility will be reviewed based on standard of care testing done for the elective index procedure. Adverse events (AE) will be monitored and recorded daily throughout the subjects' hospital stay and again at their post-surgical follow-up visits (30 day) and at 6 month and 1 year (part of standard of care) either in person or through review of subjects' EHRs and phone interviews. These will be reviewed individually by the PI and co-investigators and reported by study personnel. An adverse event log will be created for this study. Regularly scheduled meetings of study personnel will take place to review study progress, procedures, AEs and safety considerations. Real time management of AEs will be done per standard of care by the subjects' health care providers. Any serious AE or unanticipated problems will be reported to the Springfield

Committee for Research Involving Human Subjects (SCRIHS) in accordance with SCRIHS policy.

Specification of Safety Parameters: Safety of exparel and marcaine will be evaluated in this study. Safety endpoints will include:

- (1) Adverse events including serious adverse events (SAEs), suspected ADRs, and discontinuations due to AEs
- (2) Physical examination
- (3) Vital signs

Table 1: Schedule of study assessments

Assessment	Baseline/ Screening	Pre-op (D0)	OP (D0)	Each POD	hospital discharge	F/UP (D30 ± 7d)	F/UP (6m)	F/UP (12m)
Inclusion/exclusion	X	X						
ICF	X							
Vitals	X		X	X	X	X	X	X
PE (done as standard of care by any authorized clinical team member)	X		X	X	X	X	X	X
Medical/Surgical History	X							
Concomitant medications (excluding pain Rx)	X	X	X	X	X	X	X	X
Pain/opioid medication log	X	X	X	X	X	X	X	X
Randomization		X						
Study drug administration			X					
Pain-VAS	X		X	X*	X*	X	X	X
Incentive spirometry (done at bedside)			X	X	X			
MEQ**			X	X	X	X	X	X
Complications			X	X	X	X	X	X

*On POD1 and later, pain assessment will be done as is standard of care by hospital staff until discharge.

** Calculation of MEQ using <http://clinicalcalc.com/Opioids/>

References:

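### Section 3.4.1 allows randomisation the night before surgery, but Table 1 puts both the last eligibility check and randomisation on Day 0, and nothing requires the check to come first

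*Combined protocol and SAP*

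**What the plan says.** Five parts of the combined protocol and SAP bear on this.

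- **Section 3.4.1 (Summary), timing.** "Subjects will be randomized to one of two groups, test (A) and active control (B), Night or morning of scheduled surgery". The evening before is the natural reading of the night option, although the word 'before' does not appear.
- **Section 3.4.1, eligibility.** "After the patient voluntarily agrees to participate (sign ICF), their inclusion/exclusion criteria will be reviewed again". This precedes the randomisation sentence and carries no Day-0 timing.
- **Table 1 (end of section 7).** The row "Inclusion/exclusion" is marked at Baseline/Screening and again at Pre-op (D0). Randomisation is marked at Pre-op (D0) only.
- **Section 3.4.4 (2).** The subjects and study statisticians are blinded, but "the surgical team and coordinators will not be blinded". The schedule for all 200 patients "will be listed on one list that will be provided to MMC pharmacy and will also be stored by the Research Coordinators for reference".
- **Section 3.4.6 (1).** A patient who takes narcotics after screening and before the day of surgery "will be classified as screen failure (if not randomized) or withdrawn (if randomization has been done".

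Section 3.3 counts withdrawals within a loss allowance of 50 out of 200. Section 5 defines no analysis population.

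**The concern.** A patient found ineligible before assignment is not part of the randomised comparison. Once assigned, the same patient uses an entry on the list, and removing that patient breaks the randomised set. If those who judge the failure know the arm, removal can differ between arms, by intent or not.

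The one criterion with a written withdrawal rule is narcotic use shortly before surgery. The primary outcome is opioid consumption over 72 hours, so this criterion is plausibly related to it. There is also room for judgement. Exclusion criterion 7 exempts narcotics given for standard diagnostic procedures before screening, and section 3.4.6 repeats no such exemption for the period after screening. Section 3.4.1 allows in-patients to be enrolled, so narcotic exposure close to surgery is conceivable.

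The exposure looks avoidable. Study drug is given at the end of the operation, and the documents give no reason for assigning the arm the evening before.

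**Working it through.** **1. Order of events under each timing option**

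| | Morning of surgery | Night before |
|---|---|---|
| Agrees with Table 1 (randomisation at D0) | Yes | No |
| D0 check can precede assignment | Yes, but not required | No |
| Staff can know the arm from the assignment when the D0 check is made | Only if assignment is done first | Yes |
| Narcotic use since screening, found at the D0 check | Screen failure if not yet assigned; withdrawal if assigned | Withdrawal |
| Another criterion found to fail after assignment | No rule given | No rule given |
| Conversion to open thoracotomy (exclusion criterion 14) | After assignment | After assignment |

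The handling of a patient with the same narcotic history therefore depends only on when randomisation was done. The last row does not change with timing.

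**2. Does timing alone decide who knows the arm?** No. Section 3.4.4 gives the coordinators the full list, so they can know the next assignment before any check, whenever randomisation takes place.

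**3. Is sample size affected?** The inputs from section 5 are d=0.862, d=0.6825 and d=0.5, power 0.90 for the first two, alpha 0.05, and the Wilcoxon rank-sum test. Sidedness is not stated, and two-sided is used here. With n per arm and the efficiency of the Wilcoxon test under normality, 3/π:

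N = n × 3/π, df = 2N − 2, noncentrality = d × √(N/2), with power taken from the noncentral t distribution.

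- d=0.862 at power 0.90 gives 31 per arm (stated 31).
- d=0.6825 at power 0.90 gives 49 per arm (stated 49).
- d=0.5 with 75 per arm gives N = 71.6, noncentrality = 0.5 × √35.8 = 2.99 and power 0.844 (stated 0.84).
- 150 / (1 − 0.25) = 200 (stated 200).

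All the stated figures reproduce.

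The documents give no rate of late eligibility failure. As an assumption, take 2% to 10% of all 200: 0.02 × 200 = 4 and 0.10 × 200 = 20. This is generous, because it treats every patient as assigned the night before. Both counts fit within the 50 allowed. If total losses stay at or below 50, power at d=0.5 is at least 0.844. If such withdrawals came on top of a fully used allowance:

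| Extra losses beyond 50 | Per arm | Power at d=0.5 |
|---|---|---|
| 5 | 72.5 | 0.832 |
| 10 | 70 | 0.818 |
| 20 | 65 | 0.789 |

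The point is therefore mainly about selection after assignment, not about numbers.

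**The case against.** The strongest reply is that section 3.4.1 already gives the order consent, eligibility review, randomisation, and that Table 1 is compatible with checking first on the morning of surgery. That is fair. It shows that the late check is a possibility left open, not the planned sequence. It does not close the gap, because the night option stands in the text and the table has a further check on Day 0.

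A second reply is that reordering alone achieves little. While the coordinators hold the list, a check made before assignment can still be made with the next arm known. Selective removals might then appear as screen failures outside the randomised set, where they are harder to see. This stands, and it is why the remedy needs more than a change of timing.

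A third is that many criteria, such as age, earlier surgery on the same side, or allergy, are unlikely to change overnight. That also stands, and it limits the likely number of cases.

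A reader might infer more than the documents support in two ways:

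- **That every patient who fails the D0 check is withdrawn.** Section 3.4.6 says so only for narcotic use. For other criteria there is no rule.
- **That the bias can be sized by supposing the heaviest opioid users of one arm are removed.** The D0 check comes before the operation, so the 72-hour outcome does not yet exist and nobody can select on it. Any real shift depends on how well pre-operative information predicts later use, and the documents do not give that. Such a calculation yields an unattainable upper bound and should not be set against the planning effect.

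**Conclusion.** The point holds as a gap and an inconsistency. Sections 3.4.1, 3.4.4 and 3.4.6, read with Table 1, permit an avoidable removal after randomisation, on a criterion plausibly linked to the primary outcome, by staff who can know the arm. How often this would happen and how much bias would follow cannot be estimated from the documents. No power deficit follows while losses stay within the allowance.

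The conclusion rests on two readings: that the night option means the evening before, and that withdrawn patients do not count as evaluable. Section 3.3 implies the second, but section 5 does not state it. The point is modest in size and worth acting on because the change is small.

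**What to change.** 1. In section 3.4.1, reconcile the timing with Table 1. Suggested wording: Randomisation takes place on the day of surgery, only after the Pre-op (D0) inclusion/exclusion check has been completed and recorded; a failure found at that check is a screen failure.
2. In section 3.4.4 (2), withhold the allocation list from the coordinators who enrol until eligibility has been recorded. Without this, step 1 does not protect against selection.
3. In section 5, state that patients withdrawn after assignment will be counted and reported by arm, with the reason. Conversion to open thoracotomy belongs in this count, since it remains a post-randomisation exclusion under either timing.

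**Cost.** A few sentences. Pharmacy would learn the assignment on the morning of surgery instead of possibly the evening before. Study drug is given only at the end of the operation, which suggests this is workable, but the documents state no pharmacy lead time, so this should be confirmed with pharmacy first. The sample size does not change.

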3.4.2. Informed consent

All participants will be required to provide written informed consent. The study staff will introduce the study to potentially eligible patients. The principal or co-investigators and/or study coordinators will review the informed consent document with the subject. The subject will be provided information related to the study purpose, procedures, potential risks and benefits to participation, voluntary nature of their potential participation and provide them an opportunity to ask and have all questions answered prior to obtaining any signature. A study investigator will be available to answer any questions. Subjects will not be compensated for participation and there are no additional research-related costs to subjects for participation in the study. Both medications and the surgery are standard of care and will be billed accordingly.

3.4.3. Treatments to Be Administered

(1) Prescribing information

- Bupivacaine- epinephrine 0.25%, 1:200,000 (Marcaine): See Drug Insert (submitted)
 - i. 0.25% concentration up to 225mg with epinephrine administered as an subcutaneous injection at the port site
 - Final dosing will be determined by the physician based on patient weight and is individualized on a case by case basis.
 - Maximum dosage : 400 mg/24 hours
- Bupivacaine liposomal 1.3% (Exparel): See Drug Insert (submitted)
 - i. Up to 266 mg (20 mL) administered as a subcutaneous injection at the port site, diluted to a final concentration of 2.22mg/mL with 100mL normal saline (0.9%).

- Final dosing will be determined by the physician based on patient weight and is individualized on a case by case basis.
- Maximum dosage: 266 mg (20 ml)

(2) Labeling of Investigational Products

Pharmacy will dispense the investigational drug per randomization assignment and labelled per hospital standards. These are FDA-approved products that are both used as standard of care.

(3) Storage of Investigational Products

Investigational products will be stored in the Memorial Medical Center Pharmacy per hospital guidelines. Accountability for Investigational Products

Accountability of the investigational products will be achieved per Memorial Medical Center guidelines by MMC staff as done per standard protocol

3.4.4. Method of treatment assignment/Randomization

(1) Subject Numbering

Subjects will be assigned a unique consecutive subject number, 3 digits. Preceding the digits will be the letters EM (Exparel/Marcaine) to identify the study. For example, subject numbers will be EM001, EM002, etc., in consecutive order. Subject numbers, once assigned, will not be reused.

(2) Randomization

A randomization schema will be performed by a secondary statistician at the Centers for Clinical Research for all 200 patients and will be listed on one list that will be provided to MMC pharmacy and will also be stored by the Research Coordinators for reference. The patient ID and randomization assignment will be sent to the pharmacy along with screening weight of the subject. The subject(s) and study statistician(s) will remain blinded to the treatment assignments throughout the course of the study while the surgical team and coordinators will not be blinded. Data will be analyzed by the blinded statistician(s) to ensure minimal bias.

(3) Administration and timing of Study drug

Study drug will be administered by the investigator surgeon or members of surgical team under supervision of the investigator surgeon as described below:

Test group A: At the end of the surgical procedure patients in group A will receive injections of liposomal bupivacaine (Exparel, standard dose based on patient's screening weight) delivered via a 25 gauge needle into the surrounding cutaneous and deep tissue including the periosteum around the thoracoscopic port incision sites after closure.

Active Comparator Group B: At the end of the surgical procedure patients in group B will receive, injections of standard bupivacaine HCl with epinephrine 0.25% delivered via 25 gauge needle into the surrounding cutaneous and deep tissue including the periosteum around the thoracoscopic port incision sites after closure.

- *Rationale for Selection of Doses*

Dose will be calculated by the physician based on the screening weight of each randomized patient as is done in the standard way. This will provide reasonable comparison of standard dose of each drug that would have been given for any individual patient.

(4) Treatment compliance

Treatment compliance will be measured in terms of the subject receiving an injection of either Exparel® or Marcaine with epinephrine® from the study personnel. No other forms of compliance will be measured.

Reasons for any deviation from the administration of less than 100% of the investigational products dose must be recorded in the subject's medical records.

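### Unblinded coordinators who may take consent also hold the full list of 200 assignments, and no step conceals upcoming assignments, so selection bias is possible if the list is used in order.

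*Combined protocol and SAP*

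**What the plan says.** Under section 3.4.4(2), a secondary statistician prepares the schema for all 200 patients. It "will be listed on one list that will be provided to MMC pharmacy and will also be stored by the Research Coordinators for reference". Subjects and study statisticians stay blinded, "while the surgical team and coordinators will not be blinded". The handoff is described as follows: "The patient ID and randomization assignment will be sent to the pharmacy along with screening weight of the subject". The sender is not named.

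Section 3.4.4(1) adds: "Subjects will be assigned a unique consecutive subject number, 3 digits". No rule ties a line of the list to a subject number.

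On enrolment, section 3.4.2 says: "The principal or co-investigators and/or study coordinators will review the informed consent document with the subject". Section 3.4.1 says that after consent "their inclusion/exclusion criteria will be reviewed again" against standard-of-care testing, without naming who does it. Randomization follows, "Night or morning of scheduled surgery". In "Table 1: Schedule of study assessments", the inclusion/exclusion and randomization rows are both marked in the Pre-op (D0) column, with no order between them.

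No section mentions sealed envelopes, a central or web release, or pharmacy-only custody. No block size or stratification is given.

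**The concern.** Allocation concealment means that whoever decides on a patient's entry cannot know the arm that patient would get. Here a role that may take consent holds every assignment in advance. If lines are used in order, a coordinator who has followed enrolment can read the next one. A borderline patient can then be entered, deferred or judged ineligible with the arm in view, knowingly or not.

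The setting makes this more than theoretical. Section 1.1 says the choice between the two drugs currently rests on physician preference, and section 2 states a directional hypothesis. Patients' likely opioid need is partly visible before surgery, and opioid use over 72 hours is the primary outcome. Blinding the subject and the analyst does not help, because the distortion occurs at entry. The planned rank-sum test in section 5 has no covariate adjustment.

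**Working it through.** **Step 1. Who can know what, and when.**

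- *List holders:* the pharmacy and the Research Coordinators (3.4.4(2)). The text does not separate the Research Coordinators from the study coordinators of 3.4.2, and does not bar list holders from enrolling.
- *Direction of the handoff:* the assignment goes to the pharmacy with the patient ID, although the pharmacy already has the list. Someone outside the pharmacy therefore has the assignment first.
- *Consent:* less exposed. Randomization comes later, and with several patients waiting the line that will apply may not yet be known.
- *Eligibility re-review after consent:* exposed if the line can be foreseen.
- *Pre-op (D0) check:* the clearest exposure, since it shares a column with randomization and no order is given.
- *Room for judgement:* age, ALT/AST and creatinine limits are fixed. Extensive narcotic use in the month before screening has no threshold (exclusion 7), and substance-abuse history rests on investigator opinion (exclusion 18).

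**Step 2. Reproduce the plan's power.** Section 5 gives power 0.84 for 75 per group, d = 0.5 and alpha 0.05. For a two-sided Wilcoxon test, take n' = n × 3/π, noncentrality d√(n'/2) and df = 2n' − 2. With n = 75, n' = 71.6 and the noncentrality is 0.5 × √35.8 = 2.99. Power is 0.844, which agrees. The same method returns the plan's 31 and 49 per group.

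**Step 3. False rejection under a spurious shift.** Use the same formula with no true effect and the shift s in place of d. The values of s are assumptions. Section 3.3 gives 75 per arm as the 1-year evaluable number. The primary outcome is at 72 hours, so the analysed number may be nearer 200/2 = 100 per arm.

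| s (SD) | 75 per arm | 100 per arm |
|---|---|---|
| 0.05 | 0.060 | 0.064 |
| 0.10 | 0.091 | 0.106 |
| 0.15 | 0.145 | 0.178 |
| 0.20 | 0.221 | 0.280 |

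A simulated Wilcoxon test (20,000 runs, normal data) at s = 0.05, 0.10 and 0.20 gave 0.060, 0.089 and 0.223 at 75 per arm, and 0.064, 0.102 and 0.283 at 100 per arm.

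**Step 4. How much selection produces such a shift.** Exchanging two patients between arms whose expected use differs by g SD moves the arm difference by 2g/n SD. The number of exchanges needed is s ÷ (2g/n), here for s from 0.05 to 0.20:

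| g (SD) | 75 per arm | 100 per arm |
|---|---|---|
| 1.0 | 1.9 to 7.5 | 2.5 to 10 |
| 0.5 | 3.8 to 15 | 5 to 20 |
| 0.3 | 6.3 to 25 | 8.3 to 33 |

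**Step 5. A behavioural version.** Suppose staff decline some of the worst-prognosis quarter of candidates when the next line is one particular arm. Take 75 per arm and an assumed prognosis–outcome correlation of 0.3 or 0.5 (4,000 runs each).

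| Share declined | Shift (SD) | Rejection rate |
|---|---|---|
| 25% | 0.02 to 0.04 | 0.05 to 0.06 |
| 50% | 0.06 to 0.09 | 0.07 to 0.09 |
| 100% | 0.12 to 0.21 | 0.11 to 0.24 |

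**Step 6. What removing the list changes.** With the list and lines in order, the next assignment is known with certainty. Without it, staff who know all earlier assignments in a balanced block of size 2b guess correctly a share [b + 2^(2b−1)/C(2b,b) − 1/2]/(2b) of the time. For blocks of 4 this is (2 + 8/6 − 0.5)/4 = 0.708. For one block of 200 it is 0.542. Both block sizes are assumptions.

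**The case against.** The custody facts are not open to dispute, but the consequence is less certain than they are. The plan does not say that lines are used in order, that coordinators use the list to assign, or who sends the assignment. The coordinators' copy is described as being for reference. Section 3.4.1 narrates consent, eligibility review and then randomization, and ties the review to standard-of-care testing, which narrows discretion. Exclusion 7 concerns the month before screening, so it can be settled well before the next line is known. For the interval from screening to surgery, section 3.4.6 sets a rule that needs no judgement. Section 5 plans baseline comparisons, and imbalance on recorded factors can be partly adjusted for.

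Much of this limits the argument without removing it. Exclusion 7 is a weaker example for the pre-op check than for screening. A narrated sequence does not lock eligibility before an assignment can be read, and an intended use for reference does not restrict access. Baseline comparisons cannot detect imbalance on unrecorded factors, and adjustment cannot remove it. The objection does bear on size: no figure in the documents supports any particular shift. The 1 SD exchange counts are the easiest case, and the upper end of the rejection rates needs very consistent selection.

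**Conclusion.** The concern holds. As written, the plan gives the complete allocation list to unblinded staff who may also enrol patients, and describes no concealment. This is a stated custody rule, not merely a missing detail, and confidence in it is high.

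Selection bias is possible, not shown, and depends on lines being used in order. A single list and consecutive subject numbers make that plausible. The false-rejection rates of 6% to 22% at 75 per arm and 6% to 28% at 100 per arm are illustrations on assumed shifts. Modest selection would add little to the nominal 5%. The point must be fixed because the validity of the randomized primary comparison depends on it and later analysis can repair only part of any damage.

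**What to change.** In section 3.4.4(2):

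- Delete the part of the custody sentence that gives the coordinators a copy. State that only the generating statistician and the pharmacy hold the list.
- Replace the handoff sentence. Once consent and the final pre-op eligibility check are recorded, the coordinator sends the pharmacy only the patient ID and screening weight. The pharmacy takes the next unused line, records date and time, and dispenses.
- If blocks are used, do not disclose their sizes to enrolling staff.
- In Table 1 or its notes, state that the pre-op eligibility check is completed before randomization.

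Coordinators may be unblinded after each assignment.

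The cost is a short amendment and a changed pharmacy handoff. Pharmacy cover is needed at the night or morning randomization time, and the documents do not say whether it exists. If it does not, a web release or sealed envelopes, under the same rule that eligibility is recorded first, would serve the same purpose. The sample size is unchanged.
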